## 4 STUDY ENDPOINTS

### 4.1 Hierarchical multiple testing

A hierarchical multiple testing procedure will be used to evaluate superiority of the primary endpoint, followed by the evaluation of superiority of the key secondary endpoints. A fixed sequence stepwise multiple testing procedure at the 0.05 level will be performed in the following pre-specified hierarchical order:

- I. Primary endpoint: change from baseline ALSFRS-R score after 48 weeks.
- II. Key secondary endpoint: CAFS at 48 weeks
- III. Key secondary endpoint: Survival time (death, tracheostomy or initiation of non-invasive ventilation for more than 20 hours a day for more than 10 consecutive days) over 72 weeks

Each step will be considered confirmatory if all previous steps were successful (i.e. if superiority was achieved). If any of the previous steps were unsuccessful, the subsequent steps are regarded as exploratory.

### 4.2 Primary endpoint

The primary endpoint is the change from baseline in Amyotrophic Lateral Sclerosis Functional Rating Scale – Revised (ALSFRS-R) score after 48 weeks.

### 4.3 Secondary endpoint(s)

All secondary endpoints will be analyzed at 48 weeks including all patients, and additionally at 72 weeks for the subset of patients who reach 72 weeks (or ICE) as a subgroup analysis. The exception will be the planned main analysis for the key secondary endpoint of survival time (see below). This analysis will include data up to 48 weeks for all patients and up to 72 weeks for the subgroup of patients with planned extended follow-up. Analyses conducted at earlier time-points are informative but of lower relevance.

#### Key secondary endpoints

- Combined assessment of function and survival (CAFS) at 48 and 72 weeks;
- Survival time, i.e. time to death, tracheostomy or initiation of non-invasive ventilation for more than 20 hours a day for more than 10 consecutive days, over 72 weeks.

#### Efficacy

- Change from baseline in ALSFRS-R score after 24, and 72 weeks;
- The slope of the decrease in ALSFRS-R score over time at 24, 48 and 72 weeks;
- Change from baseline in ALSFRS-R score after 24, 48 and 72 weeks on:
  - Bulbar function (question 1-3 of the ALSFRS-R);
  - Fine motor function (question 4-6 of the ALSFRS-R)
  - Gross motor function (question 7-9 of the ALSFRS-R)
  - Respiratory function (question 10-12 of the ALSFRS-R)
- Time to a 3, 6, 9 and 12 points change from baseline in ALSFRS-R score;
- Proportion of subjects with change from baseline in ALSFRS-R score at 24, 48 and 72 weeks in categories: categories will include change  $\geq 0$ , change between  $< 0$  and  $\geq -1$ , change between  $< -1$  and  $\geq -2$  etc.;
- Time to change in staging of disease progression (King's staging system and MiToS) or death over 72 weeks;
- Overall survival: Proportion of subjects alive (survival rate) after 24, 48 and 72 weeks;
- Proportion of subjects alive and no tracheostomy, or no initiation of non-invasive ventilation for more than 20 hours a day for more than 10 consecutive days after 24, 48, and 72 weeks;
- Change from baseline in slow vital capacity (SVC, liters) at 24, 48 and 72 weeks;
- Change from baseline in the overall mega score for the hand-held dynamometer (HHD) at 24, 48 and 72 weeks.

### QoL

- Change from baseline in the total score on the ALS Assessment Questionnaire-40-Item (ALSAQ-40) Form at 24, 48 and 72 weeks;
- Change from baseline in EuroQoL – 5 Dimensions-5 Levels (EQ-5D-5L) questionnaire score at 24, 48 and 72 weeks.
- Change from baseline in Health related QoL Visual Analogue Scale (VAS) score at 24, 48 and 72 weeks.

### Cognition

- Proportion of subjects with a change of  $\geq 8$ ,  $\geq 4$ , and  $\geq 9$  for ALS Specific, ALS Non-Specific, and ECAS (Edinburgh Cognitive and behavioural ALS Screen) total score;
- Change from baseline for ALS Specific, ALS Non-Specific, and ECAS total score at 24, 48 and 72 weeks;
- Time to a mean change of  $\geq 8$ ,  $\geq 4$ , and  $\geq 9$  for ALS Specific, ALS Non-Specific, and ECAS total score.

### Pharmacokinetics

(Population) PK parameters of FAB122 and riluzole

#### **4.4 Exploratory endpoint(s)**

### Pharmacokinetics

PK interaction between FAB122 and riluzole

 Defined as tracheostomy due to trouble breathing as per item 12 of the ALSFRS-R.

## Biomarkers

- Change from baseline in the prognostic ALS biomarkers neurofilament light (NFL) and heavy chain (NFH)
- Change from baseline in the surrogate ALS biomarkers creatinine and creatine kinase
- Change from baseline in the surrogate ALS biomarker Urinary extracellular domain of neurotrophin receptor p75 (Urinary P75ECD)
- Change from baseline of oxidative stress biomarker 8-hydroxyguanosine (8-OHdG)

## Health economics

Cost-Utility analysis of treatment with FAB122.

## **4.5 Safety endpoint(s)**

- Nature, frequency and severity of Treatment Emergent Adverse Events;
- Parameters derived from vital signs and 12-lead electrocardiogram (ECG);
- Parameters derived from laboratory tests (hematology, biochemistry, urinalysis);
- Proportion of subjects that drop out due to adverse events.

# **5 STATISTICAL ANALYSIS**

## **5.1 General considerations**

Raw data (in listings) will be presented in the same precision as received. Appropriate rounding will be performed for the summary statistics: arithmetic mean, median, SD (standard deviation) and confidence limits will be presented with one more decimal than the original data; minimum and maximum values will be presented with the same precision as the original data. In frequency tables, percentages will be presented with 1 decimal. P-values will be presented with 3 decimals, and those smaller than 0.001 will be replaced by <0.001.

Descriptive statistics presented in general summary tables will be the number of non-missing observations (n), mean, SD, minimum, median and maximum for quantitative data. For categorical data, frequency counts and percentages will be determined. The denominator when calculating percentages will be the number of patients in the applicable analysis population. Descriptive statistics will be displayed for all visits that a measurement is collected on, even if the endpoint is only referring to limited visits for the analysis.

Baseline is defined as the last value measured prior to first study treatment administration, unless otherwise specified. In case this value is missing for a specific patient, but an earlier measurement (e.g. screening) is present, this value will be used as baseline instead. Unscheduled measurements are excluded as baseline value.

If available in the database, data for screening failures will not be presented in summary tables, except for disposition and end-of-study displays. Data for screening failures will be listed as available.

For patients that are unable to attend the clinic on a study visit due to ALS progression, at least ALSFRS score, AEs and concomitant medication data are collected. These data may be collected by telephone and are considered of the same quality as performed during live visits.

If a patient is not able to attend the site for two consecutive visits, then IMP will be discontinued at the 2nd missed visit, but participation in the trial and data collection can continue via telephonic visits to collect ALSFRS-R, AE and concomitant medication. It is assumed that data collected via telephone visits is of same quality as the data collected via site visits.

For QoL questionnaires: in case of technical issues with the ePRO device, these can be completed on a paper version as a backup. The data collected per paper are considered of the same quality as collected with the ePRO device.

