## 2.4 Sample size

The sample size estimation is based on the primary endpoint: the change from baseline in ALSFRS-R score after 48 weeks. A difference of 3.0 points between FAB122 treatment arm and placebo is assumed with a (pooled) standard deviation of 7.5 and an allocation ratio of 2:1 (FAB122:Placebo). With these assumptions, a total sample size of 300 (200 patients on FAB122 and 100 on placebo) is needed to achieve 90% power to detect the difference of 3.0 points between the two treatment groups at a 5% (2-sided) level of significance.

For further details on the background of these assumptions, refer to the protocol.

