5. The DSMB will assess the results of the NCS for the first enrolled 60 patients (about 40 active and 20 placebo). The NCS will be conducted for the first enrolled 60 patients at screening, and on weeks 4, 12, and 24. Then according to the evaluation by the DSMB, one of the following options will be performed: 1) If no neurological concerns are observed, the study will continue with one additional NCS at week 48 for the first 60 patients. Then for the next enrolled patients, one NCS will be performed at Screening and another one at week 48. Additional NCS(s) could be performed between Screening and week 48 if any abnormality is detected by the neurological examination or any suggesting symptoms of neuropathy are reported by the patient. 2) If NCS show signs of neurological damage, intensive NCS monitoring will continue for all patients at Screening and on weeks 4, 12, 24, 36, 48, 60, and 72.
6. Hematology: hematocrit, hemoglobin, RBC (red blood cell count & parameters), WBC (white blood cell count inclusive differential count), platelet count. Biochemistry: total protein, alkaline phosphatase, AST (aspartate transaminase), ALT (alanine transaminase), GGT (Gamma-glutamyl transpeptidase),

7. Vitamin B6 levels will be monitored and, if necessary, supplementation of vitamin B6 (pyridoxine (100 mg/day)) will be prescribed.
8. Urinalysis: Blood, Glucose, Protein, Specific gravity, Ketone, pH, Nitrite, Leukocytes, Bilirubin, Urobilinogen, Microscopic exam, if abnormal results are noted.
9. Blood sampling for FAB122 PK analysis will be done in ~90 subjects in selected sites. Of those ~30 subjects will participate in a PK profiling sampling schedule and the additional ~60 subjects will participate in a population PK sampling schedule. Sampling schedule for PK profiling: pre-dose and 15 min, 30 min, 1, 1.5, 2, 4 hrs., and 6hrs. after the FAB122 morning dose. The pre-dose sample may be collected within 30 minutes prior to dosing, the samples taken 15 and, 30 min post dosing samples should be taken within ±2 minutes of the scheduled time, the 1 hr. post dosing sample within ±5 minutes, the 2-hour sample within ±10 minutes and the 4 hr. and 6hr. sample within ±20 minutes of the scheduled time. The time of sampling will be accurately recorded. Sampling schedule for population PK: (1) pre-dose (within 1 hour prior to dosing), (2) within 5- and 30-minutes post dosing, (3) 1 hour and (4) 1.5 hour after the second PK sample was taken.

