##### **3.1.4 Safety (SAF) population**

The SAF population includes all randomized patients who have received at least one dose of the investigational drug, irrespective of satisfying other criteria. This population will be used for the analysis of safety and tolerability, and statistical analysis will be done “as treated”.

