- **Per Protocol and ITT Analysis:** This analysis will include patients from the PP and the ITT analysis sets. The same missing data imputation and ICE strategy as for the mITT analysis will be applied to these sensitivity analyses.

For presentation of descriptive statistics of efficacy data, no imputation or sensitivity analysis will be included, and data will be presented ‘as is’. All these analyses will be done on data available at the visit considered. In summary tables, the number of patients without missing data will be presented (per visit, if applicable) unless otherwise specified. In calculations of percentages, the denominator will be the number of patients in the applicable analysis population.

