## **5.7 Safety and tolerability evaluation**

All safety presentations will be created using the SAF population.

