### **5.7.7 Nerve conduction study (NCS)**

NCS consists of the following assessments: Hand Temperature (°C), Foot Temperature (°C), SRAR, SNAP (µV) and SCV (m/s). The latter two have been determined for locations Median Nerve, Ulnar Nerve, Radial Nerve, Sural Nerve. Descriptive statistics will be presented for all assessments, irrespective of being performed per NCS protocol or quality assessment result. The following descriptive displays will be presented:

- Descriptive statistics per visit and treatment arm, including change from baseline.
- Mean +/- SD plots versus time
- Shift from baseline categories (presenting frequencies and percentages per visit and treatment arm)
- Percentage drop >50% from baseline (presenting frequencies and percentages per visit and treatment arm)
- Normal/abnormal classification results (presenting frequencies and percentages per visit and treatment arm)

Information on high/low/normal categorization is presented in section 9.1.

In case of multiple measurements for a specific visit, repeats have occurred because of a measurement being not quality approved. In those instances, the last repeated value will be used for the descriptive statistics. All collected values will be listed.

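### By-visit categorical safety tables divide by the whole safety population, so NCS and late urinalysis percentages count patients not due for a test as not abnormal

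*SAP*

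**What the plan says.** **Denominator.** SAP 5.1: "The denominator when calculating percentages will be the number of patients in the applicable analysis population". SAP 5.2, in its part on missing efficacy data, repeats the rule: "In calculations of percentages, the denominator will be the number of patients in the applicable analysis population". Just before that, it promises to show how many patients have data, by visit where that applies. That promise stands in a paragraph about efficacy tables.

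**Population for safety.** SAP 5.7: "All safety presentations will be created using the SAF population". SAP 3.1.4: "The SAF population includes all randomized patients who have received at least one dose of the investigational drug". The planned size comes from SAP 2.4: "a total sample size of 300 (200 patients on FAB122 and 100 on placebo) is needed to achieve 90% power".

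**Tables affected.** SAP 5.7.7 asks for three categorical NCS displays by visit and arm: shifts between categories, normal/abnormal status, and "Percentage drop >50% from baseline (presenting frequencies and percentages per visit and treatment arm". SAP 5.7.2 asks for urinalysis frequency tables by treatment and time, and SAP 5.1 adds percentages for categorical data. Neither section names a denominator of its own.

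**Who is measured when.** SAP 2.5, footnote 5: "The NCS will be conducted for the first enrolled 60 patients at screening, and on weeks 4, 12, and 24". After the DSMB review there are two options. Under option 1, later patients have NCS at screening and week 48, plus extra tests if symptoms or examination findings prompt them. Under option 2, all patients have NCS at every listed visit through week 72. Footnote 1 and SAP 5.2 say that about 100 patients are followed beyond week 48.

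**The concern.** A percentage at a visit should describe the patients who were tested at that visit. Under this rule the numerator can come only from tested patients, while the denominator also holds patients whom the schedule never called for testing. They are counted as not abnormal.

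This matters most for NCS. Protocol 2.2 explains that NCS was added because of neurological findings in animals at relatively low safety margins, and Protocol 9.1.4 makes significant NCS abnormalities events of special interest. A reader who takes the printed percentage as a rate would see a smaller absolute rate, and a smaller difference between arms, than was observed.

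**Working it through.** **Inputs**
- Planned safety population: 200 active, 100 placebo (SAP 2.4 and 3.1.4).
- NCS at weeks 4, 12 and 24: first 60 patients, about 40 active and 20 placebo (SAP 2.5, footnote 5).
- Follow-up after week 48: about 100 of 300 (footnote 1; SAP 5.2), which is about 67 active and 33 placebo at 2:1.

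**Plan's own figure.** Difference 3.0, SD 7.5, two-sided 5%, 90% power, 2:1. Placebo n = (1 + 1/2) × (1.960 + 1.282)² × 7.5² / 3² = 98.5, so 99 placebo + 198 active = 297. With 100 and 200, power = Φ[3 / (7.5 × √(1/100 + 1/200)) − 1.960] = Φ(1.306) = 0.904. The planned 300 is reproduced, so 200 and 100 are sound bases for the denominators.

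**Dilution factor** = safety population N / number due for the test at the visit.

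| Table and visit | Due (active / placebo) | Denominator under the rule | Factor |
|---|---|---|---|
| NCS weeks 4, 12, 24, first 60 only, option 1 | 40 / 20 | 200 / 100 | 5.0 |
| NCS week 48, either option | all | 200 / 100 | 1.0 |
| NCS weeks 60, 72, option 2 only | 67 / 33 | 200 / 100 | 3.0 |
| Urinalysis weeks 60, 72 | 67 / 33 | 200 / 100 | 3.0 |

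SAP 6 reports 3 patients randomized but not treated. If the safety population is 297, the factors are 297/60 = 4.95 and 297/100 = 2.97.

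**Illustrations (all counts assumed)**
- One arm: 4/40 = 10% prints as 4/200 = 2%.
- Two arms: 8/40 against 1/20 is 20% against 5%, a difference of 15 points and a ratio of 4. It prints as 8/200 against 1/100, which is 4% against 1%: a difference of 3 points and still a ratio of 4.
- Week 60 or 72: 20/100 = 20% prints as 20/300 = 6.7%.

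**Sensitivity to the NCS schedule.** The protocol's rationale for NCS (section 2.1) and its visit lists (section 6.3) give NCS at weeks 4, 12 and 24 without limiting it to 60 patients. If everyone is tested, the design-driven NCS factor at those weeks is 1.

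An intermediate case assumes that 300 patients are recruited evenly over 10 months and all are tested until the DSMB review. Sixty are enrolled by month 2, and the last of them reaches week 24 (5.52 months later) at month 7.52.
- Week 4: 30 × (7.52 − 0.92) = 198 tested, factor 1.5.
- Week 12: 30 × (7.52 − 2.76) = 143 tested, factor 2.1.
- Week 24: 60 tested, factor 5.0.

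Missed visits would add to any of these. If 17% of the patients due were not assessed (assumption), 5.0 and 3.0 become 5.0/0.83 = 6.0 and 3.0/0.83 = 3.6.

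**The case against.** The best defence is that little information is lost. Frequencies are printed beside the percentages, so a reader who knows the schedule can rebuild the rate. SAP 5.7.7 also gives quantitative NCS summaries by visit and arm, with non-missing n under SAP 5.1, plus mean plots and full listings. Significant NCS abnormalities appear again as events of special interest. The design-driven dilution is about equal in both arms, no NCS hypothesis test depends on it, and the table shells are in a separate document (SAP 10.1) that may handle it.

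Most of this is right and limits the harm. It does not remove the problem: the rule is explicit, nothing in the SAP overrides it for safety tables, and the promise of a per-visit n is made only for efficacy. Equality between arms is also only approximate. Protocol 11.4 expects more discontinuation on active treatment (adverse events 7% against 3%, lack of efficacy 10% against 5%). If those patients missed the visit, an equal 10% rate would print as 10 × 0.83 = 8.3% on active and 10 × 0.92 = 9.2% on placebo. This is an assumption, since the plan intends to keep following them.

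A second objection concerns the remedy. Footnote 5 allows symptom-triggered NCS, and SAP 5.7.7 pools assessments whether or not they followed the NCS protocol. Dividing simply by everyone assessed could therefore overstate the rate. For ALSFRS-R change categories it would also restrict the table to survivors. Both points stand, and the fix is limited accordingly.

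**Conclusion.** The point holds for by-visit categorical safety tables. From the schedule alone, NCS category percentages at weeks 4, 12 and 24 print at as little as one fifth of the observed rate. This requires that NCS at those weeks was done only in the first 60 patients and that option 1 was followed. Urinalysis categories at weeks 60 and 72 print at about one third, as would NCS at those weeks under option 2. It should be corrected, but it is a reporting fault and does not threaten the trial's conclusions.

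Four stronger readings may suggest themselves, and the documents do not support them:
- *Both factors hit routine NCS.* The five-fold factor needs option 1, which schedules no routine NCS after week 48. NCS at weeks 60 and 72 needs option 2, which tests all patients.
- *Week-72 efficacy percentages are diluted three-fold.* SAP 4.3, 5.6.2 and 10.3 put those results in the separate 100-patient subgroup.
- *ALSFRS-R and staging percentages are wrong because they do not sum to 100%.* With the non-missing n shown, as SAP 5.2 promises, this is a presentation convention.
- *The trial's neurotoxicity safeguard is disabled.* The DSMB reviews NCS under its own SAP and charter (SAP 1 and 5.4), which this rule does not govern.

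Adverse event incidence, quantitative summaries and the primary test are outside this effect.

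**What to change.** Add one exception to SAP 5.1 and carry it into the shells for SAP 5.7.2 and 5.7.7:
- In by-visit categorical safety tables, the denominator is the patients scheduled for the assessment at that visit and assessed there. Shift and >50% drop tables also require a baseline value. Print that n for each visit and arm.
- Show symptom-triggered or otherwise unscheduled NCS in a separate display, so that selected patients do not raise the scheduled-visit rate.
- Keep the population denominator for adverse events, medications and disposition. Leave the efficacy categories as they are.
- State which NCS schedule was followed, and reconcile Protocol 2.1 and 6.3 with footnote 5 and Protocol 8.2.5, since this determines who counts as scheduled.

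The cost is a SAP sentence, a programming default and one more NCS display. Denominators will vary by visit. No new data are needed, and neither the primary analysis nor the testing hierarchy changes.

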## 5.2 Missing or excluded data or intercurrent events

### *Efficacy data – intercurrent events*

The intercurrent events during the study can be broadly classified as terminal and non-terminal intercurrent events. Death or “real” loss to follow-up are considered terminal intercurrent events, wherein there is absolutely no data available for these patients after the occurrence of the event. The other intercurrent events are non-terminal, where there is a possibility of collecting data from these patients after the occurrence of the intercurrent event (ICE).

Note that per design of the study, only 100 patients will be followed until week 72. The non-available data for the ~200 patients between week 48 and 72 will not be considered as ICE.

Regarding intercurrent events, following ICH E9 (R1), two types of strategies will be applied for the primary statistical analysis performed for the primary endpoint and utilizing the primary analysis population (mITT).

The “Treatment Policy” strategy will be applied to the following intercurrent events:

- Treatment discontinuation due to adverse events.
- Treatment discontinuation due to lack of efficacy.
- Other unforeseen treatment related reasons (i.e. due to efficacy or safety issues).
- Rescue medication.
- Non-treatment-related reasons, other than those already specified earlier. This includes situations like patients moving to another location for treatment unrelated reasons. Note that the “Treatment Policy” strategy might not be applicable if there are real lost-to-follow-up cases after doing all efforts to retrieve the data.

For deaths, the Treatment Policy cannot be applied, and missing data imputation will be used for the statistical analyses.

The “Treatment Policy” strategy implies that the efficacy observed assessment (including those collected after the occurrence of the intercurrent event) will be used regardless of the occurrence of an intercurrent event.

The “Composite” strategy will be applied to the following intercurrent events.

- Related death (or death with unknown reasons). It is expected that the rate of death at 52 weeks will be lower than that observed in the trial (<17%). A non-substantial but lower rate is expected in the experimental arm.
- “Real” lost to follow-up. These are cases where there is lost to follow-up after reasonable attempts to contact the patient have been made and all efforts to retrieve the data have failed.

The “Composite” strategy for handling these events will be applying a conservative scenario using the 95% worst percentile combined with multiple imputation (the intercurrent event is explicitly taken into account and made part of the outcome by this imputation, conditioned on timepoint). This method uses the imputation of a conservative value representing the 95th worst percentile.

